12.6. Health Economic Endpoints

The health economic data might be collected locally to support local regulatory requirements. The analyses, if conducted, will be described in a separate analysis plan and reported separately.

13. Health-related Quality Of Life Analysis

13.1. Rationale

Health-related quality of life is a multidimensional construct, which can be defined as a state of general well-being reflecting physical, psychological, and social well-being and the impact of the disease and/or treatment related symptoms on daily-life functioning. The subject's subjective perspective is an inherent component of HRQoL and is therefore best assessed via self-administration.

Reducing mortality and morbidity is still the most important factor in cancer clinical research.

Nevertheless, issues such as reducing side effects, symptom relief and improving subjects' satisfaction have also become relevant parameters in the evaluation of medical strategies. Cancer treatments may produce adverse effects and diminish a subject's quality of life even when survival is extended. Progress in the acceptance of new cancer therapies is sometimes critically dependent on their HRQoL consequences.

Particularly in glioblastoma multiforme (GBM) subjects, who suffer from an incurable disease with a median OS of slightly more than a year despite intensive treatment, the balance between quantity and quality of survival gain due to (experimental) treatment is pivotal. If treatment-related side effects influence the HRQoL of these subjects in a negative way, possible gains in terms of progression-free or overall survival will have to be balanced against the burden of treatment. It is for this reason that HRQoL is included as a secondary endpoint in the current study of newly-diagnosed GBM subjects.

13.2. Objective

The main objective of HRQoL assessment within this trial is to determine the impact of addition of MRZ to TMZ and RT therapy on five chosen domains being primarily global HRQoL, with fatigue, physical function, neurocognitive function, communication and motor dysfunction as secondary HRQoL outcomes. It is expected that these are likely to be most affected in subjects, based on the toxicity profiles and information of previous studies. The Ho hypothesis will be tested that there is no difference between subjects in both arms during and after treatment regarding global HRQoL. A secondary objective is to evaluate the effect of the treatment on the remaining symptoms and functioning scales as treatment-related side effects may have a (temporary) negative influence on the health-related domains of HRQoL of these subjects.

13.3. HRQoL Instrument

Health-related quality of life will be assessed with the EORTC Quality of Life Questionnaire (QLQ-C30) version 3. This instrument is composed of multi-item and single-item scales. These include five functional scales (physical, role, emotional, social, and neurocognitive), three symptom (fatigue, nausea and vomiting and pain) and a global health status/QoL scale and six single items (dyspnea, insomnia, appetite loss, constipation, diarrhea and financial difficulties).

All scales and single items meet the standards for reliability. The reliability and validity of the questionnaire is highly consistent across different language-cultural groups. The average time to complete the questionnaire is approximately 10 minutes. While this standard is used in EORTC studies, it lacks some dimensions that pertain to the QL issues in certain brain cancer. Therefore, we will also use the EORTC Brain Cancer module (QLQ-BN20), designed for use in brain tumor subjects undergoing protocol treatment or radiotherapy. It includes 20 items assessing visual disorders, motor dysfunction, communication deficit, future uncertainty, as well as other specific symptoms, such as headaches, seizures or drowsiness. A retrospective validation study has been performed confirming the psychometric validity of this questionnaire (Cocks K, 2012). The threshold for minimal clinically important difference will be used as recommended in the published literature for EORTC QLQ-C30 and QLQ-BN20 (Maringwa J, 2011).

13.4. Study Design

Subjects are eligible for the HRQoL assessment in this study if they fulfill the eligibility criteria (see chapter 3 of the protocol). Should the subject refuse to fill out the form, then this should exclude the subject from further participation in the study. Subjects will be informed in the subject informed consent form that they will have their HRQoL assessed regularly while involved in this trial. In this Phase 3 study, HRQoL will be evaluated in a longitudinal design in all subjects entered in both arms of the study. The HRQoL questionnaires must be filled out at the hospital when subjects come for a scheduled visit according to the EORTC “Guidelines for administration of questionnaires” (see appendix F of the study protocol). The pretreatment questionnaires must be filled within 2 weeks before start of treatment. Subsequent questionnaires are administered after the end of combined chemo- and radiotherapy, and subsequently coinciding with the MRI visits and MMSE schedule in both treatment arms, also after tumor progression. Master copies of the HRQoL questionnaires will be sent to the participating institutions. The clinical report forms will include a question whether the HRQoL forms have been filled in, and if not, the reason why. The questionnaire will be handed out to the subjects by the investigator or a study nurse prior to seeing the doctor for clinical evaluations. The subject should complete the questionnaires by her/himself in her/his own language during the visit as completely and accurately as possible. It is recommended that a key person (e.g. research nurse) at each center should be responsible for questionnaire data collection in order to optimize the compliance of the subject and to ensure the completeness of the data.

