## 8.4 Follow-up analysis

Further to the recommendations of the IDMC, the patient recruitment had to be prematurely closed. The final number of randomized patients was 749 (750 planned). The results of this study had also to be prematurely disclosed. The interim analysis was considered as the final analysis of this study.

All randomized patients will be followed till the total number of OS events for the initially planned final analysis was observed (488 deaths). At that date, a follow-up analysis will be performed in accordance to the updated Statistical Analysis Plan for descriptive purpose only, with more mature data for all endpoints.

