## 10.4 Study design

Patients are eligible for the QOL assessment in this study if they fulfill the eligibility criteria (see chapter 3). Should the patient refuse to fill out the form, then this should exclude the patient from further participation in the study. Patients will be informed in the patient informed consent form that they will have their QOL assessed regularly while involved in this trial. In this phase 3 study, QOL will be evaluated in a longitudinal design in all patients entered in both arms of the study.

The QOL questionnaires must be filled out at the hospital when patients come for a scheduled visit according to the EORTC “Guidelines for administration of questionnaires” (see Appendix F). The pre-treatment questionnaires must be filled within 2 weeks before start of treatment. Subsequent questionnaires are administered after the end of combined chemo- and radiotherapy, and subsequently coinciding with the MRI visits and MMSE schedule in both treatment arms, also after tumor progression.

Master copies of the QOL questionnaires will be sent to the participating institutions. The clinical report forms will include a question whether the QOL forms have been filled in, and if not, the reason why. The questionnaire will be handed out to the patients by the investigator or a study nurse prior to seeing the doctor for clinical evaluations. The patient should complete the questionnaires by her/himself in her/his own language during the visit as completely and accurately as possible. It is recommended that a key person (e.g. research nurse) at each center should be responsible for questionnaire data collection in order to optimize the compliance of the patient and to ensure the completeness of the data.

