### 3. What instructions should be given to the patient?

At entry in a study, the RP should give the patient an explanation of the objective of the study and instructions for completing the questionnaires.

The patient should be informed that participation in the QOL protocol is voluntary and that the information provided is confidential (identification is only for administrative purposes and includes date of birth and today's date (completion date)).

The following issues should be explained to the patient:

- The schedule of assessments.
- The questionnaire is a self administered questionnaire that should be completed by the patient him(her)self. The patient can ask for aid in reading or writing but should not let another person provide the answers.
- The patient should circle the choice that best corresponds to his/her situation.
- There is no right or wrong answer to any of these questions. The answers will not influence any medical decision making.
- All questions should be answered.
- The patient will be given a questionnaire in the default language(s) of the hospital. If desired, the patient may request another language. The RP will then contact the EORTC Headquarters for the appropriate translation.

The RP should make sure that the patient understands the instructions.

At each subsequent assessment as defined by the protocol, the patient should receive the questionnaire from the RP or from other appropriate staff if the RP is unavailable.

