#### **6. Review of the completed questionnaire**

After the patient has completed the questionnaire, the person handling the questionnaire should:

- Complete the “Hospital Staff” specific data box.
- Check that the completion date is correctly filled in by the patient.
- Screen the questionnaire for omissions.

*If this is the case:*

- Please ask the patient the reason for omissions. It may be that patient forgot to flip a page or did not understand a question. The patient should not be forced to provide an answer if (s)he does not wish to do so.
- Additional explanation may be provided, but the questions should not be rephrased.

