#### **7. Missing forms**

If for some reason the patient is unable or does not wish to complete a quality of life questionnaire the reason and the date of visit should be documented on the corresponding CRF (case report form).

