6.2.3. Per-Protocol Population

The PP includes all randomized subjects who are eligible and have started their randomized treatment arm. Subjects with major protocol deviations as defined in the medical review plan are also excluded from the PP population.

Subjects who did not receive MRZ or TMZ, with or without RT are excluded from PP and SP.

Patients excluded from PP or SP will be reported in separate tables with the reason(s) of exclusion.

7. Subject Disposition

Subject disposition summary (number and percentage of subjects) will be presented on all subjects who are enrolled. The number of subjects will be summarized by investigator site and overall.

- Subjects who were enrolled
- Subjects who were screen failures
- Subjects who were randomized
- Subjects who took at least 1 dose of study drug (MRZ/TMZ)
- Subjects who discontinued the study drugs

Listing for screen failure reasons/ineligibility will be provided.

A summary of subject disposition will be presented by treatment arm for the following analysis populations:

- ITT
- SP
- PP

The number of subjects completing the study according to the protocol will be also displayed.

Reasons for **treatment discontinuation** will be summarized for all ITT subjects with the following categories:

- Completed
- Progressive disease (PD)/relapse/death due to PD
- Adverse events (AEs)
- Withdrawal by subject
- Physician's decision
- Protocol deviation
- Death
- Other malignancy
- Lost to follow-up
- Pregnancy
- Other (specify, including discontinuation of study drugs further to IDMC decision)

Reasons for **completing the study follow-up/study** (i.e. no more follow up visit and no longer participating in the study) will be collected on the eCRF and will be summarized for ITT subjects with the following categories:

- Death
- Lost to follow-up
- Withdrawal by subject
- Other (specify, including discontinuation of study drugs further to IDMC decision)

Listings will be provided for ITT subjects randomized but not treated, and for treated subjects who discontinued treatment with reason for treatment discontinuation highlighting discontinuation of study drugs further to IDMC decision.

8. Protocol Violations

The protocol violations were identified and assessed by clinical research physician or designee following EORTC standard operational procedure. The protocol violations will be summarized overall and by treatment arm in the ITT population and for the unmethylated MGMT stratum.

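### The rule that refusing a QoL form ends study participation contradicts the plan's voluntary-QoL and missing-form rules and, read literally, its survival follow-up

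*SAP*

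**What the plan says.** Protocol 10.4 says "Should the patient refuse to fill out the form, then this should exclude the patient from further participation in the study", and SAP 13.4 repeats the sentence with subject in place of patient: "Should the subject refuse to fill out the form, then this should exclude the subject from further participation in the study". Neither restricts it to a time point. Forms are due at baseline, at the end of radiotherapy and then every 16 weeks. Protocol 6.3.2.2 and 10.4.1 and SAP 13.5 continue them until death. The Protocol summary stops them at the start of new anticancer treatment if that comes first.

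Both sections refer sites to Appendix F of the protocol for administering the questionnaires. Item 3 there says "The patient should be informed that participation in the QOL protocol is voluntary". Item 6, on omitted answers, says "The patient should not be forced to provide an answer if (s)he does not wish to do so". Item 7 deals with the case where "the patient is unable or does not wish to complete a quality of life questionnaire" and requires only that "the reason and the date of visit should be documented on the corresponding CRF".

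On follow-up, Protocol 8.4 says "All randomized patients will be followed till the total number of OS events" planned for the final analysis (488 deaths), and SAP section 2 says the same. SAP section 7 describes a patient who has left the study as "no more follow up visit and no longer participating in the study".

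**The concern.** A site cannot obey both instructions. One makes refusal of a form a reason to leave the study; the other makes it a missing form with a recorded reason. Because forms keep falling due after randomisation, the rule as worded reaches patients already in follow-up for the primary endpoint. If a site followed it, survival time after the refusal could go unobserved.

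Patients who decline a questionnaire may be those who are deteriorating. The trial is open label, and the IDMC reported severe neurological and neuropsychiatric disorders with marizomib (Protocol 1.2.1). A link between refusal, prognosis and arm is therefore plausible, and censoring with such a link is informative.

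**Working it through.** **1. The passages side by side**

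| Place | Consequence of not completing a form |
|---|---|
| Protocol 10.4, SAP 13.4 (refusal sentence) | Excluded from further participation |
| Same sections, a few lines later | CRF records that the form is missing, and why |
| Appendix F, items 3, 6, 7 | Voluntary; no forcing; reason and visit date recorded |
| Protocol 10.5.3, SAP 13.6.3 | Analysed as missing data; exploratory analysis only if compliance is below 50% (protocol) or 70% (SAP) |
| Protocol chapter 3 | Not an eligibility criterion |
| Protocol 5.4, SAP 5.1 | Not listed as a reason to stop study treatment |
| SAP 7 | Not a named reason for leaving follow-up |

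The refusal sentence stands alone against the rest of the plan.

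**2. How it could reach the endpoints**

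SAP 7 equates leaving the study with no further follow-up visits. OS is then censored at the last date known alive (SAP 11.2). PFS is censored at the last adequate assessment when a patient discontinues the study for reasons other than progression or death (SAP 15.2). The ITT set is unaffected (Protocol 8.2.1, SAP 6.2.1). The possible harm is therefore early censoring.

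**3. The plan's own figures, as a base**

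Inputs from Protocol 8.1.1 and 8.3: 488 deaths, HR 0.74, one-sided alpha 0.015, 1:1 allocation.

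- Power before the futility look = Φ(|ln 0.74| × √488 / 2 − z₀.₉₈₅) = Φ(3.326 − 2.170) = 87.6%.
- Adding the futility look (88 deaths, stop if HR > 1.12, final alpha 0.01499) by simulation gives 86.1%, against 86% stated.
- The uMGMT subgroup (320 deaths, HR 0.70, alpha 0.01) gives 80.6%, against 80.7% stated.

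These figures are not in dispute.

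**4. Loss unrelated to prognosis or arm**

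Assumptions: exponential survival with medians 16 and 21.6 months; accrual of 150 in year 1, then 400 per year; a fraction q of both arms lost to OS follow-up at month 2.3, 6.0 or 9.7 (about weeks 10, 26 and 42). The fraction q is not in the documents.

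| q | Deaths at month 49 | Month of 488th death | Single-look power at month 49 |
|---|---|---|---|
| 0% | 503 | 47.3 | 88.6% |
| 2% | 496 | 48.1 | 88.2% |
| 5% | 485 | 49.3 | 87.4% |
| 10% | 467 | 51.7 | 86.1% |
| 20% | 432 | 58.0 | 83.1% |

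Because the analysis is event-driven, the cost is mainly time.

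**5. Loss related to prognosis and arm, no true effect**

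Assumptions: a fraction f of each arm has g times the hazard of the others (whose median is 16 months). All of these patients in the marizomib arm are lost at 2.3 months, and none in the control arm. Entries are the simulated OS HR without loss → with loss. The no-loss value differs from 1 only by simulation error.

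| f | g = 1 | g = 2 | g = 3 |
|---|---|---|---|
| 2% | 1.006 → 1.006 | 1.006 → 0.995 | 1.006 → 0.992 |
| 5% | 1.006 → 1.006 | 1.005 → 0.980 | 1.005 → 0.973 |
| 10% | 1.006 → 1.005 | 1.005 → 0.956 | 1.005 → 0.943 |

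For scale, SE(ln HR) at 488 deaths is about 2/√488 = 0.091. The smallest shift with g above 1 is |ln(0.995/1.006)| = 0.011, or 0.12 SE. The largest is |ln(0.943/1.005)| = 0.064, or 0.70 SE.

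A second null simulation let refusals occur at progression in both arms. It assumed a median of 7 months to progression, half the patients with shorter survival after progression and four times the refusal probability, and OS censored at progression for refusers. The HR was 0.97 with 5% (control) against 10% (marizomib) refusing, 0.93 with 10% against 20%, and 1.00 with equal rates. Together the two exercises show that bias needs a link to prognosis and a difference between arms.

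**The case against.** The sentence does not mention survival follow-up, and more specific text protects it. A patient who stops treatment early must still be followed for disease and survival unless consent for those data is withdrawn, and must then be asked about survival-only contact (Protocol 5.4, SAP 5.1). Survival status is collected until death after progression (Protocol 6.3.2.2). This stands. It shows what the plan intends elsewhere, so early censoring is a possible result of the sentence and not a planned one.

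The sentence follows directly on a statement of who is eligible for the QoL assessment, so an entry condition on the baseline form may have been meant. That is plausible, but chapter 3 has no such criterion and the wording is not limited to baseline. Recruitment has closed at 749, so an entry condition has no patient left to act on; only the post-randomisation reading can still have an effect.

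The practical reach is small. The primary analysis keeps the 28 April 2020 cutoff, with 106 deaths reported at the IDMC review, and the later analysis is descriptive. The modelled bias favours marizomib, so it cannot explain the IDMC's finding of no evidence of benefit. All of this stands and limits the consequence. It does not remove the contradiction.

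**Conclusion.** The contradiction is certain and rests on the text alone: two sections make refusal a ground for exclusion, while Appendix F and the missing-form handling treat it as missing data. The conflict with survival follow-up of all randomised patients arises if the sentence is applied literally after randomisation.

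A reader might go further and infer that the rule removes randomised patients from OS follow-up selectively and breaks the ITT principle. The documents do not support that. ITT keeps every randomised patient, other sections require survival follow-up, and nothing states that refusals occurred or differed by arm or prognosis. Nor should the simulated hazard ratios be read as estimates for this trial. Their refusal rates, arm differences, prognostic links and complete loss of later survival data are all assumptions. Losing every worse-prognosis patient from one arm and none from the other is an extreme choice.

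The size of any bias is therefore unknown. It would be nil under no true effect if refusal were unrelated to prognosis or equal between arms. Any future effect falls mainly on the descriptive long-term analysis. Exclusions made before the April 2020 cutoff, if there were any, could also touch the primary analysis.

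**What to change.** In Protocol 10.4 and SAP 13.4, replace the refusal sentence so that it agrees with Appendix F, items 3, 6 and 7. After randomisation, a refused questionnaire is a missing HRQoL form with its reason recorded. The patient remains in the ITT population and in OS, PFS and safety follow-up unless consent for those data is withdrawn.

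If completing the baseline form was meant as a condition of entry, it belongs in Protocol chapter 3. With recruitment closed, that would only document past practice, so it cannot replace the sentence above.

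In the disposition tables (SAP 7), report by arm how many patients left follow-up after refusing a form, with the date of last contact. These patients would otherwise be hidden under withdrawal by subject or other. If the count is zero or very small, the concern for OS and PFS is closed.

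The cost is one sentence in each document and one count. No sample size, alpha or analysis method changes.

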13.5. HRQoL Schedule

The time windows for eligible HRQoL assessments will be as follows:

Assessment	Time window
Baseline	No earlier than 14 days before randomization and no later than the day of randomization itself.
At the end of radiation therapy	No earlier than day of last radiation therapy treatment and no later than the first day of TMZ maintenance administration
During TMZ/MRZ maintenance: every 16 weeks	Every 16 weeks during TMZ maintenance \pm 7 days (at MRI scan visit).
After TMZ/MRZ maintenance: every 16 weeks until death	Every 16 weeks \pm 7 days. (at MRI scan visit)

13.6. Statistical Considerations

The primary HRQoL endpoint that is considered relevant for this study is the Global health/QoL status scale of the QLQ-C30 instrument. The secondary HRQoL endpoints will be the fatigue, physical function, neurocognitive function, communication and motor dysfunction scales. Other scales from QLQ-C30 and QLQ-BN20 will be analyzed on an exploratory basis. The “financial difficulties” scale of the QLQ-C30 will not be analyzed at all.

The sample size calculation has been performed based on OS data. This is the primary endpoint and therefore no calculation has been performed based on changes in HRQoL. The primary HRQoL endpoints that are considered relevant to this trial are detailed above. The HRQoL data will give information to support or reject the null hypothesis that there is no difference between patients in both arms during and after treatment.

Data will be scored according to the algorithm described in the EORTC scoring manuals for the corresponding instruments. All scales and single items are scored on categorical scales and linearly converted to 0-100 scales.

Primary and sensitivity analyses will be performed in the ITT population and in the uMGMT stratum.

